7.9 Notification to the Sponsor of Events Requiring Immediate Reporting

Throughout the study, the Investigator must document all AEs on the eCRF in a timely manner. IREs, as defined in [Section 7.8.2](#), are events that must be reported immediately to MacroGenics Product Safety or designee within 24 hours of being identified.

The Investigator must immediately complete and fax/email the *Immediately Reportable Event (IRE)* Report Form within 24 hours of identifying the event to MacroGenics Product Safety/designee. The IRE Report Form and IRE Report Form Completion Guidelines are found in the Study Procedures Manual.

For pregnancy, the MacroGenics Pregnancy Exposure Form must also be completed and faxed/mailed. The Investigator must attempt to follow the pregnancy to term or termination

in order to report on outcome and health status of mother and child. The Pregnancy Exposure Form is found in the Study Procedures Manual.

7.10 Emergency Unblinding

Not applicable. This is an open-label study.

7.11 Efficacy and/or Pharmacokinetic and Pharmacodynamic Assessments

7.11.1 Efficacy Assessments

7.11.1.1 Treatment of Patients According to Principles of Immune-Related Response Criteria

Tumor assessments will be obtained at screening using CT and/or MRI scans at time intervals as specified in the [Appendix 1](#) (Time and Events Table). The study is divided into 6 Tumor Assessment Cycles; the first is a 6-week cycle called the Initial Tumor Assessment Cycle and Cycles 2 through 6 are 9-week cycles. The tumor assessment takes place at the end of each cycle. Treatment will continue until patients have completed study therapy and required follow-up, experienced disease progression, or have been withdrawn from the study (see [Section 4.4](#) and [Section 5.3](#)). At each on-treatment tumor assessment time point, the objective response status will be determined. In the context of the statistical analysis for this trial, objective response determination and the assessment of best overall response (BOR) will be defined using both conventional RECIST1.1 criteria ([Appendix 5](#)) as well as an adaptation of these criteria, designated as immune-related response criteria (irRC) (i.e., irRECIST as defined in [Appendix 6](#)). Patient management decisions, however, will be made solely based on the immune-related response criteria ([Appendix 6](#)).

For patients who demonstrate acceptable tolerability of treatment with MGA271, and an objective response assessment of irCR, irPR or irSD, or unconfirmed clinically-stable irPD, therapy may be continued (see [Section 4.4](#) and [Section 5.3](#)).

For patients who are otherwise clinically stable, but have met conventional criteria for PD, therapy may be continued at the discretion of the investigator pending confirmation of progression at the next scheduled tumor assessment. This approach allows for limited treatment of patients beyond the initial radiographic documentation of disease progression, assuming that patients are tolerating therapy adequately, that patients remain otherwise clinically stable despite this initial radiographic evidence of disease progression and that the Investigator feels the patient may still derive benefit from continuation of therapy. Treatment of patients according to irRC (i.e., irRECIST) principles is supported by well-documented evidence that in some patients treated with T cell directed, immune-modulatory agents, their tumors can evolve to an objective response after an initial period characterized by either apparent radiographic growth of target lesions or the development of new target lesions that would otherwise meet the criteria for disease progression using conventional response criteria ([67](#))

For patients in whom progression is confirmed at the next scheduled tumor assessment, the criteria for immune-related PD (irPD) will have been met, and treatment with MGA271, pembrolizumab, or MGA012 should be discontinued. The patient should be removed from study participation after completion of protocol specified follow-up (see [Section 8.3](#) and [Appendix 1](#)). For patients who experience an objective response of immune-related complete response (irCR) or immune-related partial response (irPR), responses will be considered unconfirmed until the response has been documented by a subsequent confirmatory scan obtained no less than 4 weeks after the initial scan demonstrating an objective response.

7.11.1.2 Objective Response and Response Duration

Target and non-target lesions will be designated and evaluated using both conventional RECIST 1.1 criteria ([Appendix 5](#)) and immune-related response criteria ([Appendix 6](#)) as noted above for the purposes of statistical analysis. Objective responses will be categorized as CR, PR, SD, or PD for conventional RECIST 1.1 criteria and irCR, irPR, irSD, and irPD for the immune-related response criteria. Determination of the objective response rate will be calculated based on the proportion of response evaluable patients achieving CR or PR using the respective criteria, when such responses are confirmed by a subsequent scan obtained at least 28 days after the initial documentation of objective response. Response-evaluable patients will include those patients who have measurable disease and have had a baseline tumor assessment and at least 1 on-treatment tumor assessments (see [Appendix 1](#)). Objective responses that are not subsequently documented with a confirmatory CT or MRI scan (e.g., unconfirmed responses) will not be included as an objective response for the purpose of calculating overall objective response rates. Response duration will be calculated from the time of initial response (CR or PR) documentation (in patients who have a subsequent confirmation of objective response) to the time of progressive disease or death, whichever occurs first.

A patient's response duration will be censored if at the time of last antitumor assessment response is ongoing. Patients who discontinue study treatment for a reason other than progressive disease may be followed for efficacy until 1 of the following occurs: the patient progresses, withdraws consent for follow up, or initiates other anti-cancer therapy, or the overall trial is closed.

7.11.1.3 Progression-free Survival (PFS)

PFS will be calculated as the time from the date of the first dose of study drug until the date of any documented PD; the date of death from any cause, or date of last assessment for tumor progression, whichever occurs first ([Appendix 3](#)). A patient's PFS will be censored if at the time of last assessment for progression, the patient remains progression free. PFS will be determined using both conventional RECIST 1.1 and irRC (i.e., irRECIST) criteria.

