4.1 Overall Study Design and Plan

4.1.1 General Study Design

This study is a Phase 1, open-label, dose escalation and cohort expansion study designed to characterize the safety, tolerability, PK, PD, immunogenicity, and preliminary antitumor activity of MGA271 administered IV weekly in combination with pembrolizumab administered IV every 3 weeks (Q3W). Beginning with Amendment 5, this study will also characterize the safety and tolerability of MGA271 in combination with MGA012 (anti-PD-1 antibody), both administered by IV, Q3W, through the addition of a new cohort, Cohort 4.

The study consists of a **Dose Escalation Phase** to determine the MTD or MAD (if no MTD is determined) of MGA271 administered in combination with 2 mg/kg pembrolizumab, followed by a **Cohort Expansion Phase** to further define the safety and initial efficacy of the combination with the MGA271 dose established in the first phase. The study treatment schema is presented in **Figure 2**.

Figure 2 MGA271 + Pembrolizumab Treatment Schema

a Patients may receive up to 5 subsequent 9-week treatment cycles of MGA271 + pembrolizumab depending on response to study treatments

*All patients will enter an Efficacy Follow-up Period after receipt of the last dose of study treatment to be followed for up to 24 weeks for survival.

[figure not shown]
MGA271 will be administered as an IV infusion over 120 minutes on a once-weekly schedule. Pembrolizumab will be administered at 2 mg/kg as an IV infusion over 30 minutes every 3 weeks. On the days that both agents are administered, pembrolizumab will be administered first, followed by MGA271.

For both the Dose Escalation and Cohort Expansion phases, patients' first tumor assessment will be obtained on Cycle 1 Study Day 42 of the **Initial Tumor Assessment Cycle**.

Patients who remain clinically stable and do not experience unacceptable toxicity that necessitates permanent discontinuation of the study drugs, at the completion of the Initial (6-week) Tumor Assessment Cycle will be eligible to receive additional treatment with pembrolizumab and MGA271. Assuming that the patient remains clinically stable, maintains a response status of SD or better, and does not experience unacceptable toxicity that necessitates permanent discontinuation of the study drugs, patients may receive up to 5 additional 9-week treatment cycles during **Subsequent Tumor Assessment Cycles**, for a maximum total of 51 doses of MGA271 and 17 doses of pembrolizumab.

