Appendix 3 Definition of PFS

Situation	Date	Outcome
No baseline tumor assessments	Date of 1 st dose	Censored
Death prior to the 1 st scheduled tumor assessment	Date of death	Progressed
No post-baseline tumor assessments in absence of death prior to the 1 st scheduled tumor assessment	Date of 1 st dose	Censored
Documented disease progression	Date of disease progression	Progressed
Initiation of alternative anti-cancer treatments in absence of PD	Date of last tumor assessment prior to initiation of such treatment	Censored
Death or progression immediately after missing two or more consecutive scheduled tumor assessments	Date of last tumor assessment prior to missed assessments	Censored

**Appendix 4 Eastern Cooperative Oncology Group (ECOG)
Performance Status**

Grade	Description
0	Fully active, able to carry on all pre-disease performance without restriction.
1	Restricted in physically strenuous activity, but ambulatory and able to carry out work of a light or sedentary nature (e.g., light house work or office work)
2	Ambulatory and capable of all self-care, but unable to carry out any work activities. Up and about more than 50% of waking hours.
3	Capable of only limited self-care, confined to bed or chair more than 50% of waking hours.
4	Completely disabled. Cannot carry-on any self-care. Totally confined to bed or chair.
5	Dead

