5 ENDPOINTS AND COVARIATES

5.1 Efficacy Endpoints

Response will be categorized as complete response (CR), partial response (PR), stable disease (SD), or progressive disease (PD) and evaluated using RECIST 1.1 criteria and as immune-related complete response (irCR), immune-related partial response (irPR), immune-related stable disease (irSD), or immune-related progressive disease (irPD) using irRC. The ORR will be the proportion of patients in the response evaluable population achieving CR or PR when such responses are confirmed at least 28 days after the initial observation of an objective response. A two-sided 95% exact binomial confidence interval will be calculated around the ORR for each expansion cohort.

Duration of response (DoR) will be calculated for responders as the time from initial response (CR or PR) to the time of PD or death, whichever occurs first. Kaplan-Meier methods will be used to estimate DoR over time and the median DoR. Responders who complete the study without documented PD will be censored at the date of their last tumor assessment.

PFS and irPFS will be calculated as the time from the initial infusion of pembrolizumab or MGA271 until documented disease progression, or death from any cause. Patients with no PFS event (disease progression or death from any cause) will be censored at the date of their last tumor assessment. In addition, PFS and irPFS rates will be calculated at 3-month and 6-month year time points from the first dose of study drug. Kaplan-Meier methods will be used to estimate PFS over time and the median duration of PFS. The method of Brookmeyer and Crowley (1) will be used to construct 95% CIs around PFS estimates of the median and other quartiles for each expansion cohort.

Incomplete and missing data can complicate interpretation of PFS. **Table 3** describes the handling of these data for the PFS analysis.

Overall survival (OS) is defined as the time from the initial infusion of pembrolizumab or MGA271 to death from any cause. Kaplan-Meier methods will be used to estimate the overall survival function. Patients who do not die will be censored at the date that the patient was last known to be alive. In addition, OS will be calculated at 6 months from the first dose of study drug.

Table 3 Censoring Rules for PFS Analysis

Situation	Date	Outcome
No baseline tumor assessments	Date of 1 st dose	Censored
Death prior to the 1 st scheduled tumor assessment	Date of death	Progressed

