6.6.3 Time-to-Event Analyses

Kaplan-Meier methods will be used to estimate cumulative probabilities and quartiles (25th percentile, median, and 75th percentile) of time-to-event endpoints (DoR, PFS, irPFS, and OS). The method of Brookmeyer and Crowley (1) will be used to construct two-sided 95% CIs around the quartile estimates. These calculations will be performed for all patients in cohort expansion by tumor type. Additional analysis may be carried out, by tumor type, on patients in the dose escalation cohort combined with those in the expansion cohort.

DoR will be calculated from the time of initial response (CR or PR) documentation (in patients who have a subsequent confirmation of objective response) to the time of progressive disease or death, whichever occurs first. Patients with CR or PR at time of last assessment will be censored at the time of their last tumor assessment. DoR will be calculated as follows:

DoR (months) = (progression date or death date or date of last tumor assessment – date of initial response+1) / (365.25/12)

PFS is defined as the time from first dose of study drug until documented disease progression or death from any cause, or date of last tumor assessment. A patient will be censored at the time of last assessment if the patient remains progression free at that time. Progression will be assessed using both RECIST 1.1 and irRC. PFS will be calculated as follows:

PFS (months) = (date of progression or date of death or date of last tumor assessment – date of first dose+1) / (365.25/12)

Overall survival (OS) is calculated from the time of first dose until death from any cause. Patients alive at study completion will be censored for analysis purposes. OS will be calculated as follows:

$$\text{OS (months)} = (\text{date of last contact or death date} - \text{date of first dose} + 1) / (365.25/12)$$

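### Read literally, Protocol 7.11.1.3 and SAP 6.6.3 censor PFS for a patient who dies after a progression-free scan, while SAP 5.1 and Protocol 9.5 count that death as an event

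*Protocol*

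**What the plan says.** **Wording that points to censoring**

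- Protocol 7.11.1.3 runs PFS from first dose to documented progression, death from any cause, "or date of last assessment for tumor progression, whichever occurs first". It then says: "A patient's PFS will be censored if at the time of last assessment for progression, the patient remains progression free". It refers to Appendix 3.
- The synopsis (efficacy assessments) ends PFS at progression or death only, but repeats that censoring sentence.
- SAP 6.6.3 runs PFS "until documented disease progression or death from any cause, or date of last tumor assessment", without the earliest-of clause, and adds: "A patient will be censored at the time of last assessment if the patient remains progression free at that time".

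**Wording that makes death an event**

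- SAP 5.1: "Patients with no PFS event (disease progression or death from any cause) will be censored at the date of their last tumor assessment". Protocol 9.5 and the synopsis statistical methods have the same rule.

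**Special cases**

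- In Appendix 3, "Death prior to the 1 st scheduled tumor assessment" is an event at the date of death. "Death or progression immediately after missing two or more consecutive scheduled tumor assessments" is censored at the last assessment before the missed ones. Starting other anti-cancer treatment without progression is also censored. SAP Table 3 has equivalent rows.

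**The concern.** For a patient who dies without documented progression, the last tumor assessment necessarily comes before the death. An earliest-of rule that includes the last assessment therefore selects the scan. So does a censoring rule that asks only whether the patient was progression free at that scan. The OS text shows the condition that is missing: Protocol 7.11.1.4 and SAP 6.6.3 both tie OS censoring to the patient being alive.

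Two sections of the SAP thus give different PFS data for the same patient, and 6.6.3 is the one that carries the PFS formula. PFS and irPFS medians and 3- and 6-month rates are affected. Censoring at the previous scan removes the death from the event count and treats it as uninformative, so the error can only favour the treatment. DoR in SAP 6.6.3 has a similar clash: death is an event, yet patients in response at their last assessment are censored, and a responder who dies in response fits both.

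**Working it through.** The documents give no PFS assumption or event count, so there is no planned figure to reproduce. The check is textual first, then illustrative.

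**1. One patient under each rule.** By Protocol 4.1.1 the "first tumor assessment will be obtained on Cycle 1 Study Day 42". Later scans fall every 63 days, at days 105, 168 and so on. Suppose scans at days 42 and 105 are progression free, no new therapy is given, and the patient dies on day 140. The SAP converts days to months by 365.25/12 = 30.4375.

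| Rule | Outcome | PFS |
|---|---|---|
| Protocol 7.11.1.3: earliest of 140 and 105 | Censored, day 105 | 3.45 months |
| SAP 6.6.3 censoring sentence | Censored, day 105 | 3.45 months |
| SAP 5.1, Protocol 9.5 | Event, day 140 | 4.60 months |
| Appendix 3, SAP Table 3 | No matching row | – |

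No row matches because the death is after the first scheduled scan, no scan was missed (the next was due on day 168), progression was not documented and no new therapy was started.

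**2. Twenty invented patients.** Two die on day 25. Progression is found in 6 on day 42, 3 on day 105 and 2 on day 168. Three are censored on day 231. Four die after a progression-free scan, on days 60, 75, 120 and 140.

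- Death as event: 17 events. By 3 months (day 91) 2 + 6 + 2 = 10 have failed, so PFS is 10/20 = 50%. By 6 months (day 183) 17 have failed: 3/20 = 15%. The median is reached on day 75, 2.5 months.
- Literal rule, with the four deaths censored on days 42, 42, 105 and 105: 13 events. Kaplan-Meier gives 18/20 × 12/18 = 60% at 3 months, then × 7/10 × 3/5 = 25% at 6 months. The median is reached on day 105, 3.4 months.

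**3. Simulation.** There were 20,000 patients per scenario on the protocol's scan schedule. Assumptions that are not in the documents: exponential time to first event with median 2.8, 4.0 or 5.5 months; 10%, 20%, 30% or 40% of first events are deaths without documented progression; no missed scans. Progression is dated at the next scan. Deaths before day 42 (14% to 30% of these deaths) stay events under both rules, as Appendix 3 requires. Six of the twelve scenarios, with death as event first and the literal rule second:

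| Median (months) | Death share | 3-month PFS, % | 6-month PFS, % | Estimated median (months) |
|---|---|---|---|---|
| 2.8 | 10% | 68.6, 70.9 | 25.2, 27.5 | 3.45, 3.45 |
| 2.8 | 40% | 61.3, 70.5 | 23.8, 35.3 | 3.45, 5.52 |
| 4.0 | 20% | 74.3, 78.4 | 37.9, 43.6 | 5.52, 5.52 |
| 4.0 | 40% | 71.0, 78.5 | 37.2, 49.4 | 5.06, 5.52 |
| 5.5 | 10% | 82.3, 83.9 | 49.9, 52.6 | 5.91, 7.59 |
| 5.5 | 40% | 77.3, 83.5 | 48.4, 59.9 | 5.52, 9.66 |

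Over all twelve, the literal rule is higher by 1.6 to 9.2 points at 3 months and 2.3 to 12.2 points at 6 months. The estimated median is unchanged in five scenarios, rises by 0.2 to 0.5 months in two and by 1.7 to 4.1 months in five.

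**The case against.** The strongest reply is that the intent is clear. Both 7.11.1.3 and SAP 6.6.3 name death from any cause as an endpoint, and that would do almost nothing if the last scan always won. The table row that censors deaths after two or more missed scans would be redundant for deaths. The tables are introduced for incomplete and missing data, so an ordinary death between scans may be left to the general rule in SAP 5.1. The earliest-of clause covering last assessment appears in 7.11.1.3 only. On this reading the last assessment is simply the censoring date for patients without an event.

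That is probably what was meant, and it determines the direction of the fix. It does not remove the conflict. The sentences still classify the same patient in opposite ways, and no table row decides between them.

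The second reply is scale. PFS is descriptive, and the expansion cohorts have at most 16 to 20 patients. For an assumed rate of 30% in 20 patients, the simple 95% half-width is 1.96 × √(0.3 × 0.7/20) = 0.20, or 20 points, which exceeds the shifts above. This stands as a limit on importance. The shift is nevertheless systematic, in the same direction in every cohort, and avoidable by wording alone.

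**Conclusion.** The conflict is real and should be corrected before PFS is programmed. It concerns one group: patients who die without documented progression after at least one progression-free scan, with fewer than two consecutive scans missed and no new anti-cancer therapy.

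A reader might infer more, which the documents do not support:

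- *All deaths without documented progression are censored.* Appendix 3 and SAP Table 3 make deaths before the first scheduled scan events.
- *Deaths after two or more missed scans are part of the contradiction.* SAP Table 3, which belongs to SAP 5.1, censors them too.
- *The plan has settled on censoring deaths, so reported PFS will be inflated.* The same sections name death as an endpoint. Bias follows only if the literal sentences are programmed.
- *Death between scans is the most common case.* The documents give no such frequency.

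The size, about 2 to 12 points at 6 months, is illustrative. It rests on the assumed medians and death shares, exponential event times and complete scanning. The primary safety objective and the sample size do not depend on PFS.

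**What to change.** - In Protocol 7.11.1.3, delete last assessment from the earliest-of list.
- In 7.11.1.3, the synopsis and SAP 6.6.3, reword the censoring sentence to: *patients alive and without documented progression are censored at the last tumor assessment*. In the SAP 6.6.3 definition, make clear that the last assessment is the censoring date only.
- In both Appendix 3 and SAP Table 3, add a row: death without documented progression after a progression-free assessment, with fewer than two consecutive missed assessments and no new anti-cancer therapy, is an event at the date of death.
- In SAP 6.6.3, limit the DoR censoring sentence to patients alive with ongoing response. Whether Table 3 should also govern DoR for missed scans and new therapy is a separate, optional choice.

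The cost is wording only, with no new data or patients. PFS may come out slightly less favourable than under the literal rule.

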7.11.1.4 Overall Survival (OS)

OS will be calculated as the time from the first dose of study drug until death due to any cause or last observation or contact. A patient's OS will be censored if at the time of last

contact, the patient was alive. In addition, landmark 6-month OS rate will be determined. OS will be monitored as described in the Study Manual.

